PROACTIVE OUTREACH FOR SMOKERS IN VA MENTAL HEALTH

Protocol Number: IIR 11-291-3

Funding Agency: VA HSR&D

Principal Investigator/Study Chairs:

[name], MPH and [name], MSCE

10/08/2015

ABSTRACT

Background:

Tobacco use is the leading preventable cause of death in the United States and contributes up to 24% of all VA healthcare costs. Veterans enrolled in the VA healthcare system smoke substantially more than the general population, which is particularly true among Veterans diagnosed with mental illness. Patients with bipolar disorder or schizophrenia have the highest smoking rates (69% and 58-90%, respectively) followed by those with PTSD (45-63%) and depression (31-51%). Numerous barriers exist for tobacco cessation among mental health patients, including high nicotine dependency, low rates of follow through for referrals, and limited availability of tobacco treatment tailored to their needs.

Rationale:

Most medical care providers assess tobacco use and advise smokers to quit, but they have insufficient time to follow up with treatment, leading to low long-term quit rates. Mental health providers who often meet regularly with patients report that they find tobacco cessation outside the scope of their practice and neither assess tobacco use nor refer smokers for treatment. These practice patterns have been very difficult to change even with intensive methods and across various settings and provider types. Therefore, we propose to use the electronic medical record system to identify smokers receiving mental health care and proactively reach out to engage them in treatment in line with the following aims:

Specific Aims:

1. Compare the reach and efficacy of a proactive outreach telephone-based tobacco cessation (PRO) program for patients seen in mental health to usual care (UC) advice and referral to local VA and community tobacco cessation resources.
2. Model longitudinal associations between baseline sociodemographic, medical and mental health characteristics and abstinence at 6 and 12 months in the PRO and UC conditions.

Methods:

We will use the electronic medical record to identify N=20,000 patients across 4 VA healthcare facilities who have a clinical reminder code indicating current tobacco use in the past year and who have had a mental health visit in the past 6 months. We will send each patient an introductory letter and baseline survey. Respondents will be randomized in a 1:1 fashion to intervention or control. Control participants will receive VA usual care. Intervention participants will receive proactive telephone counseling and cessation medications. We will survey participants at 2 weeks, 6 months and 12 months from enrollment. The primary outcome is cotinine-validated abstinence at the 12-month follow-up.

LIST OF ABBREVIATIONS

| | |
|-------------------|---|
| ACOS | Associate Chief of Staff. |
| COPD | Chronic obstructive pulmonary disease |
| CPRS | Computerized Patient Record System. The VA's electronic medical record system. |
| EMR | Electronic medical record. |
| FAQ | Frequently asked questions. |
| FDA | U.S. Federal Drug Administration. |
| HCS | Healthcare system |
| ICD-9 | International classification of diseases – version 9 |
| MH | Mental health |
| MHC | Mental health clinic |
| MIRECC | Mental illness research, education, and clinical center. |
| NRT | Nicotine replacement therapy. |
| PACT | Patient-aligned care teams. The VA's model for managing panels of patients, rather than individual patients. |
| PCMH | Patient-centered medical home. |
| PHS | U.S. Public Health Service. |
| PRO | Proactive outreach telephone-based tobacco cessation program. This is the name of the study arm that receives our proactive outreach intervention. |
| PTSD | Post traumatic stress disorder |
| QUERI | The VA's Quality Enhancement Research Initiative program. |
| TeleQuitMH | Telephone Quality Improvement Trial for Mental Health. This is the name of our previous research study that evaluated a telephone smoking cessation program for smokers using VA mental health clinics. |
| UC | Usual care. This is the name of the study arm that receives usual care at each site. |

Contents

| | |
|--|----|
| Protocol Title | 5 |
| 1.0 Study Personnel..... | 5 |
| 2.0 Introduction | 6 |
| 3.0 Objectives | 7 |
| 4.0 Resources and Personnel | 7 |
| 5.0 Study Procedures..... | 9 |
| 5.1 Overview | 9 |
| 5.2 Settings | 11 |
| 5.3 Identifying Potential Participants | 11 |
| 5.4 Participant Recruitment | 12 |
| 5.5 Randomization and Blinding | 12 |
| 5.6 Study Groups | 12 |

2.0 INTRODUCTION

Tobacco use is the leading preventable cause of death in the United States, responsible for 443,000 deaths per year and 8-24% of all VA healthcare costs.^{1,2} Persons with a mental health diagnosis (DSM-IV, Axis I or II), which represent about 25% of VA patients, have particularly high rates of tobacco use and consume over 46% of cigarettes sold in the U.S.^{3,4} Patients with bipolar disorder or schizophrenia have the highest smoking rates (69% and 58-90%, respectively) followed by those with PTSD (45-63%) and depression (31-51%).^{4,6} Numerous barriers exist for tobacco cessation among mental health patients, including high nicotine dependency, limited support from mental health providers, low follow through by patients with referrals, and limited availability of tobacco treatment targeted to their needs. These barriers suggest a more specialized approach to tobacco cessation with mental health populations is warranted to maximize quit rates in this at-risk population.

The overall objective of the proposed research is to address tobacco use as a chronic health condition and improve tobacco cessation services for Veterans with mental health diagnoses, which is one of the top priorities of the VA Public Health National Prevention Program. While VA primary care providers now consistently assess tobacco use and advise smokers to quit, most have insufficient time to follow up with treatment, leading to low long-term quit rates.⁷ Mental health providers often meet regularly with patients, yet report that they find tobacco cessation outside the scope of their practice and neither assess tobacco use nor refer smokers for treatment, often due to a misperception that tobacco cessation treatment would exacerbate patients' conditions.⁸ These mental health practice patterns have been very difficult to change. In our team's recently-completed research study, we have been providing telephone-based counseling customized to the needs of mental health patients referred by their mental health provider. While patient participation rates are high (65%) and the long-term abstinence rate is comparable to primary care populations (20%), referrals from mental health providers have remained significantly lower than expected. Despite consistent provider support efforts, our referrals represent only 1.5 - 9% of mental health patients who smoke.

Our central hypothesis is that we can increase the number of Veterans with mental health diagnoses who receive evidence-based tobacco cessation services by proactively enrolling them in treatment. We therefore propose a randomized, controlled trial that will use the electronic medical record system at four VA facilities to identify N=6,400 smokers receiving mental health care and contacting them via letters and telephone to offer cessation treatment. As suggested by our previous experience with this population, the treatment protocol will be targeted to the needs of mental health patients by integrating relapse-sensitive scheduling, stress reduction and problem-solving techniques, educational information, and coordination with patients' mental health providers.

3.0 OBJECTIVES

The Specific Aims of the study are to:

2. Compare the reach and efficacy of a proactive outreach telephone-based tobacco cessation (PRO) program for patients seen in mental health to usual care (UC) advice and referral to local VA and community tobacco cessation resources.
H1: We hypothesize that compared to the control group, the proactive intervention will increase the smoking abstinence rate at 12 month follow up.
3. Model longitudinal associations between baseline sociodemographic, medical and mental health characteristics and abstinence at 6 and 12 months in the PRO and UC conditions.
H2: We hypothesize that mental health distress and active substance abuse will be related to treatment uptake and long-term abstinence.^{4,9}

We will have 1-2 statisticians at the Minneapolis site responsible for designing and conducting all statistical analyses and randomization procedures, and overseeing randomization during the participant enrollment period. The statisticians will have access to PHI stored in password-protected study databases on a VA network server folder designated for this study.

Contracts

We will be contracting with the company Salimetrics. Salimetrics will be analyzing our saliva samples for cotinine (validation of our primary outcome). The study research assistants will send the saliva samples by FedEx to Salimetrics for analysis using FedEx and U.S. government guidelines for shipping biological samples. We will label the samples with a unique barcode only that contains no information that can identify participants as individuals. The VA will maintain ownership over the samples after they are sent to Salimetrics. Salimetrics will send the results of their analyses to the study's PI in an excel report sent via email to the PI's VA email address. A sample report is included in Appendix F. This file will contain no patient identifiers. Results will be labeled with the number on each sample's barcode.

[figure not shown]
5.0 STUDY PROCEDURES

5.1 OVERVIEW

Figure 1 provides an overview of our study design. We will use the EMR to identify 20,000 patients across four VA health care facilities who have a clinical reminder code indicating tobacco use in the past six months and who have had a mental health visit in the past 12 months. We will send each patient an introductory letter and baseline survey. Respondents will be randomized in a 1:1 fashion to intervention or control. Control participants will receive VA usual care. Intervention participants will receive proactive telephone counseling. For each Intervention participant, study staff will send a medication request via CPRS to the smoking cessation program at their site and primary care provider or psychiatrist as backup. Intervention participants' regular VA mental health providers will be updated on their patients' progress in treatment via CPRS progress notes and be provided with information about the program and with suggestions for how to support their patients. Control participants will receive a mailed list of local VA smoking cessation treatment options that they can access on their own or to which

they can be referred by their regular VA providers (i.e., usual care). We will survey participants at 2 weeks, 6 months and 12 months from enrollment. The primary outcome is cotinine-validated abstinence at the 12-month follow-up.

Figure 1. Overview of Study Design

5.2 SETTINGS

This study will take place at 4 sites: the VA New York Harbor Healthcare System, VA Minneapolis Healthcare System, Houston VAMC and Tampa VAMC.

5.3 IDENTIFYING POTENTIAL PARTICIPANTS

Using a three-step process, we will work with VA programmers at our Minneapolis site to identify potential participants using specific combinations of administrative data contained in the EMR system.

Selecting current smokers: Current smokers will be identified using the EMR tobacco use clinical reminder codes, where information is stored as a health factor. Patients will be included if they have screened positive for current tobacco use in the previous six months. We selected six months to reduce the false-positive rate of this sampling method (i.e., reduce the number of patients we contact who are no longer smoking). Patients will be excluded if they have an ICD 9 diagnosis of dementia (i.e., 290.XX or 331.XX).

Identifying Mental Health patients: Within the list of all eligible smokers, VA programmers will identify patients treated in the previous 12 months in a VA Mental Health Clinic, using VA clinic stop codes: 502-581.

Selecting the initial sample: After receiving a list for each site of current smokers with a recent Mental Health visit, we will select *all* women and a random sample of men to total 5,000 potential participants from each site (N=20,000) as our initial recruitment pool. We are selecting all women as an initial recruitment pool to increase the representation of women in our final sample.

Verifying the sample: We will verify our list of eligible patients each month, since we will be sending out letters and surveys to patients each month throughout the enrollment phase. If we relied solely on data collected at the beginning, smoking status could be over a year old on some subjects by the time they received their letter. Each patient who is no longer listed as a current smoker will be replaced by another patient from the site prior to mailing out any materials (and thus prior to enrollment and randomization).

Inclusion/exclusion criteria: Using administrative data and data from the baseline survey, we will verify the study's inclusion and exclusion criteria with each potential participant. Anyone who is found to be ineligible will be excluded prior to randomization and replaced with a randomly selected person from the list of current smokers for that particular site. We will thus send recruitment letters to 20,000 patients over five quarters (approximately 1400 patients per month). To maximize reach and impact we have chosen broad inclusion criteria; patients do not have to report being ready to quit within a specific time frame to enroll.

Inclusion criteria:

- Current smoker (i.e., any tobacco use in past 30 days)
- Mental Health clinic visit in past 12 months (and primary mental health diagnosis at checkout)

Exclusion criteria:

- ICD 9 diagnosis of dementia (excluded during data abstraction process)
- Does not speak English
- Does not have telephone and mailing address (necessary to mail out informed consent materials and to deliver the telephone-based intervention)

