5.9 INFORMED CONSENT PROCEDURES

There are several levels of patient information and consent for this study, which are summarized in the table and discussed below.

| Category | Type of data | Approx. n | Authorization | Comments |
|--|--|-----------|--|--|
| 1. Health system users | Administrative data 
 • Smoking status • Mental Health clinic use • Phone number • Mailing address | 40,000 | HIPAA waiver | We will randomly select 20,000 from the EMR to contact via mail for possible enrollment |
| 2. All study participants | Survey data 
 • Baseline survey • Follow-up surveys Saliva sample Administrative data 
 • Utilization • Mental health diagnoses | 3,840 | Waiver of documentation of consent | Completing the baseline survey will serve as implied consent to the telephone follow-up surveys and saliva collection, to be contacted for counseling if in the Intervention arm, and to collect follow-up administrative data from the EMR. |
| 3. Intervention treatment participants | Intervention data 
 • Counseling information • Nicotine replacement preference | 384 | Verbal consent with a waiver of documentation of consent | Participants will provide verbal informed consent prior to enrolling in counseling |

Category 1: Health System Users. The proposed study will include men and women over the age of 18 years old who smoke and have had a Mental Health visit in the past 6 months. We will

request a HIPAA waiver to obtain a limited data set from the EMR to identify eligible subjects, which is necessary to carry out the study.

Category 2: All Study Participants. Patients who complete and return the baseline survey will be participants in the study. As indicated in the cover letter and FAQ sheet, their returning the survey implies they consent to participate and no written documentation of consent will be required. After receiving the baseline survey and verifying that the respondent is still smoking, we will randomize each person to either the intervention or control group.

Category 3: Intervention Arm Participants. Intervention participants will be offered telephone counseling. Prior to starting treatment, the counselors will discuss what each treatment involves and obtain verbal consent to proceed.

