Method: The study design is a randomized block design with the blocks comprising combinations of the four hospital sites.

We will address the question of Reach via two indices:

- Proportion of patients who respond to the outreach letters and enroll in the study (i.e., completed the baseline survey). This analysis will help us understand the proportion of smokers in Mental Health who will respond to proactive outreach. Given the innovative nature of the proactive outreach approach, we will examine the acceptability of the intervention to determine which patients are more likely to accept treatment in the PRO and UC conditions. Specifically, we will use multivariable logistic regression to determine which baseline characteristics (e.g., age, race/ethnicity, income, mental health diagnosis, symptom severity) are associated with receipt of cessation counseling (state quitline or VA) or use of cessation medications.
- Proportion of patients who engage in at least one treatment session compared to control patients. Specifically, we will determine how many patients in the intervention arm used treatment (counseling and/or medications) and compare this to the number of patients

enrolled in the control arm who report using existing VA tobacco cessation services on the follow-up surveys, which will provide data regarding acceptability of treatment.

The primary smoking outcome variable that is expected to be affected by treatment is dichotomous cotinine-validated abstinence at 12 months post-enrollment. The comparisons of the abstinence rates across the two groups will be made using exact logistic regression methods, accounting for stratification by site, to model the log odds of use of smoking cessation treatment and log odds of 12-month abstinence. Exact logistic regression employs the non-parametric Chi-square test or Fisher's exact test.³⁵ These tests are widely applicable in complete randomized experimental designs that yield contingency tables. Fisher's exact test is particularly suitable for contingency tables with small and unbalanced frequency counts, which are to be expected for the population-based outcome we have chosen where our population quit rate in the control condition is expected to be 4%.

Aim 2: Model longitudinal associations between baseline sociodemographic, medical and mental health characteristics and validated abstinence at 6 and 12 months in the PRO and UC conditions.

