The power analysis is based on the primary outcome – cotinine-validated abstinence at 12-month follow-up. Our data is stratified on four hospital sites. Considering that a stratified random sample is usually more efficient than a simple random sample, to be conservative, we assume the two groups are two independent simple random samples in the following power analysis. Based on response rates during the first quarter of recruitment, we expect to receive completed surveys from 20-25% of the 20,000 patients receiving the initial mailing and 85% of respondents will be eligible (i.e., report smoking cigarettes in the prior 30 days). We will send initial mailings until we receive completed surveys from 3,840 eligible patients who will be randomly assigned to intervention and control and comprise the study population. We estimate the quit rate in the control group will be 4%. In the intervention group, about 20% of the people will accept our offer of telephone treatment, based on [name] data. We anticipate that the quit rate among Veterans

enrolled in counseling will be 16%. We are using a more conservative estimate from what we found in our recently-completed reactive recruitment study (20%) because participants will not have been directly referred from a healthcare provider. When the treatment cessation rate is combined with that from patients who do not accept treatment (assuming also a 4% quit rate), there will be a population-level quit rate of 6.4% in the intervention group, which gives us a 90% chance to detect a difference between the two groups.

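### All women but only a sample of men are mailed, so the plain reach proportion describes the mailed pool and can differ from reach among all listed mental health smokers if response varies by sex or site

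*Combined protocol and SAP*

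**What the plan says.** Section 5.3 builds the recruitment pool from each site's list of current smokers with a recent mental health visit. It takes every woman and "a random sample of men to total 5,000 potential participants from each site". The purpose is stated: "We are selecting all women as an initial recruitment pool to increase the representation of women in our final sample". With four sites, the pool is 20,000.

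Section 6.0, under the Aim 1 method, defines the first reach index as "Proportion of patients who respond to the outreach letters and enroll in the study (i.e., completed the baseline survey"). It then says what the index is for: "This analysis will help us understand the proportion of smokers in Mental Health who will respond to proactive outreach".

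The section 5.9 table puts the listed health system users at about 40,000 and describes the draw differently: "We will randomly select 20,000 from the EMR to contact via mail for possible enrollment". It does not mention that all women are taken.

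Section 6.0 contains no sampling weights, no standardization to the eligible list and no reach estimate by sex. Under Missing Data it plans to compare baseline responders with non-responders, as a check on external validity. The regression described with the reach index models receipt of treatment, not response to the mailing, and its example predictors do not include sex.

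**The concern.** Women are selected with probability 1 and men with a probability well below 1. The mailed pool therefore contains a larger share of women than the list it came from. A fixed 5,000 per site also means that a patient at a site with a short list is more likely to be mailed than one at a site with a long list. A plain proportion gives every mailed patient equal weight, so it averages response over the mix in the pool, not the mix in the population that the plan says it wants to understand.

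Reach is named beside efficacy in Aim 1, so the figure is likely to be reported and quoted. With 20,000 mailings its confidence interval will be narrow, and a modest bias could place the population value outside it. A larger mailing at the same sampling fractions would not remove such a bias.

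**Working it through.** **Inputs from the documents**
- About 40,000 listed (section 5.9 table) and 20,000 mailed (sections 5.3 and 5.9).
- Response: "we expect to receive completed surveys from 20-25% of the 20,000 patients receiving the initial mailing" (section 6.0, Power calculations).
- Eligibility: "85% of respondents will be eligible (i.e., report smoking cigarettes in the prior 30 days") (same place).
- Target enrollment: 3,840 (same place).

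**Inputs not in the documents, so assumed:** women's share of the list, f = 5–20%; difference in response between women and men, d = 2–10 points, of unknown sign.

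**The plan's own figure.** Enrollment is 20,000 × 0.20 × 0.85 = 3,400 up to 20,000 × 0.25 × 0.85 = 4,250, which brackets 3,840. Working back, 3,840 / 0.85 / 20,000 = 22.6% response, so 22.5% is a fair working value. The plan gives no weighted or sex-specific reach figure to reproduce.

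**Bias formula.** Let N be the number listed and n the number mailed. If all women are mailed, their share of the mailing is f × N/n. Then

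bias = plain − population = (share of mailed − share of list) × d = f × (N/n − 1) × d.

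With N/n = 40,000/20,000 = 2, women's share doubles to 2f and the bias is f × d. The men's sampling fraction is (20,000 − 40,000f) / (40,000 − 40,000f).

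| Women's share of list | Share of mailed | Men's fraction | Bias, d = 2 | Bias, d = 5 | Bias, d = 10 |
|---|---|---|---|---|---|
| 5% | 10% | 0.474 | 0.10 | 0.25 | 0.50 |
| 10% | 20% | 0.444 | 0.20 | 0.50 | 1.00 |
| 15% | 30% | 0.412 | 0.30 | 0.75 | 1.50 |
| 20% | 40% | 0.375 | 0.40 | 1.00 | 2.00 |

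Bias is in percentage points. It is positive if women respond more and negative if they respond less. If d = 0 it is exactly zero for any f.

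**Example.** Take f = 10%, women responding 10 points more, and a plain proportion of 22.5%. Men respond at 22.5 − 0.20 × 10 = 20.5% and women at 30.5%. The population value is 0.10 × 30.5 + 0.90 × 20.5 = 21.5%, so the plain figure is 1.0 point too high.

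**Sampling error.** At 22.5%, the standard error is √(0.225 × 0.775 / 20,000) = 0.295 points, and the 95% half-width is 1.96 × 0.295 = 0.58 points. At 21% the half-width is 0.56. Seven of the twelve cells lie below these half-widths and five lie above. A bias of 1.0 point is 1.0/0.295 = 3.4 standard errors.

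**Site.** List sizes by site are not given. As a pure illustration, take lists of 6,000, 8,000, 11,000 and 15,000 with response of 25, 23, 21 and 19%. With 5,000 mailed at each, the plain proportion is (25 + 23 + 21 + 19)/4 = 22.0%. Weighted to the lists it is (6 × 25 + 8 × 23 + 11 × 21 + 15 × 19)/40 = 21.25%. Equal lists, or equal response across sites, would give no bias from this source.

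**The case against.** A reader might infer that the reach estimate must be biased unless it is weighted. The documents do not support that. The bias is zero if response does not differ by sex or site, and they give no response rate or list share by sex and no site list sizes. In most of the scenarios above the bias is below the sampling half-width.

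It can also be said that no decision depends on this index. It is descriptive, with no hypothesis or threshold. It is not among the outcomes listed in section 5.8 and plays no part in the power calculation. A report of 22.5% in place of 21.5% would probably change no conclusion. That stands, and it limits the weight of the point.

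The sentence naming "the proportion of smokers in Mental Health who will respond to proactive outreach" can be read as a statement of purpose and not as a declared estimand. The planned comparison of responders with non-responders could reveal a sex difference, since sex was used to draw the sample. Both are fair. But that comparison yields no corrected estimate, and the sentence still invites readers to generalize.

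Two further inferences go too far. One is that the section 5.9 wording will lead the analyst to treat the sample as self-weighting: that table summarizes authorizations, and section 5.3 states the sampling openly. The other is that the weights already exist. Lists are re-verified monthly with replacement, ineligible patients are replaced from the site list, and mailing continues until 3,840 eligible surveys arrive. If every woman is already in the pool, a woman can be replaced only by a man or by a newly listed woman. The selection fractions will therefore move during recruitment.

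**Conclusion.** The point holds in a limited form. Selection is unequal by sex by design, and unequal by site if the lists differ in size. The first reach index ignores this, and its stated interpretation goes beyond the mailed pool. The plain proportion is right for that pool; for mental health smokers at the sites it is biased only if response differs by sex or site.

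Under the assumed ranges, the bias from sex is about 0.1–2.0 points in either direction. This rests on the approximate 40,000 being the sampling list. That is uncertain, because section 5.9 describes those patients by a 6-month visit window and section 5.3 uses 12 months. For another list size, the bias scales with N/n − 1.

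A reader might also infer that oversampling women undermines the trial's main result. It does not. The 12-month abstinence comparison and the second reach index (treatment use by arm) are between randomized groups and are not biased internally. This is an inexpensive improvement to a descriptive Aim 1 measure, not a threat to the primary outcome.

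**What to change.** 1. Record the numbers listed and actually mailed by site and sex throughout recruitment, including replacements.
2. Report the first reach index separately for women and men.
3. Beside the plain proportion, give an overall estimate weighted by inverse selection probability, or standardized to the eligible list, by site and sex. Say which population each figure describes.
4. Reconcile the description of the draw in the section 5.9 table with section 5.3.

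The cost is some bookkeeping, a few lines of analysis and a slightly larger standard error. For f = 10%, men carry a weight of 1/0.444 = 2.25, and the design effect from weighting is 20,000 × (4,000 + 16,000 × 2.25²) / (4,000 + 16,000 × 2.25)² = 1.06. Across f = 5–20% it runs from 1.03 to 1.17, so the standard error rises by about 1–8% (√1.03 to √1.17).
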